### **Ethical aspects**

Ethical approval was obtained from DEU Noninterventional Clinical Research Committee (Protocol number: 2014/08-19; approval number: 248; date: 4 April 2013 970-GOA) and State Hospitals Directorate. Oral informed consent was obtained from the women at the initial

interviews on the phone and written informed consent was obtained at the first home visits. At the end of the study, nursing interventions about prevention of lymphedema were offered to the control group.

In the current study, the HBM based nursing interventions offered at home visits decreased perceived barriers to lymphedema management, increased perceived benefits and improved self-efficacy in positive health behavior.

The cost of treatment for lymphedema in the intervention group was four times as low as that in the control group, which confirmed the sixth hypothesis. The finding indicated that follow-up of women having breast surgery through home visits is a cost-effective practice. Programs conducted in cooperation with public health nurses improve patient care outcomes and reduce costs for lymphedema. Sixty-seven percent of the women mention the presence of a financial burden of breast cancer treatment and 80% of the women point out to the cost of treatment for lymphedema. Treatment of breast cancer costs \$14.887-23.167 in patients developing lymphedema after breast surgery than those without lymphedema and this complication increases indirect costs due to loss of work force.

Abbreviations: EORTC QLQ-BR23, European Organization for Research and Treatment of Cancer Quality of Life Scale for Breast Cancer 23; SUPPH, Strategies Used by Patients to Promote Health; Q-DASH, Quick-Disabilities of the Arm, Shoulder and Hand Score.

**FIGURE** Consort flowchart

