### **Hypotheses of the study**

1. Extremity function restrictions will be lower in the intervention group than in the control group.
2. Self-efficacy levels will be higher in the intervention group than in the control group.
3. Functions improving the quality of life will be higher in the intervention group than in the control group.
4. There will be fewer symptoms reducing the quality of life in the intervention group than in the control group.
5. The incidence of lymphedema will be lower in the intervention group than in the control group.

6. The mean cost of the intervention group at home visits, will be lower than in the control group.

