### **Statistical analysis plan**

Data obtained in this study were analyzed with SPSS 21.0. Multifactorial variance analysis of repeated measures was used to compare the groups in terms of dependent variables, the significance test of difference between two means to compare pretest and posttest measures, one-way variance analysis of repeated measures to compare intragroup pretest and posttest measures and t-test for dependent groups with Bonferroni correction to perform further analysis of the difference between the mean scores of the groups. Intention-to-treat (ITT) analysis was utilized to eliminate effects of dropouts from the study, to maintain randomization. To prevent bias the database were analyzed by a statistician who was independent of the study.

Costs of treatments likely to be given for lymphedema in the intervention group and the control group due to the potential incidence of this condition and HBM based nursing interventions to be offered at home visits were made. The costs of the nursing interventions included time spent by the researcher at home visits, transportation for these visits, reminders on the phone, education material and tape measure. The cost of treatment for lymphedema included costs of medical treatment of an individual with stage I/II lymphedema in upper extremities in hospital. It was based on opinions of three experts. To calculate the costs from the perspective of Social Security Institution, prices of services and materials reported in Health Services Bulletin issued in Mar 2017 were taken. The expenses directly made by the patients were determined by the mean value of prices obtained from three national firms.

[figure not shown]

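### Hypothesis 6 is declared confirmed, and home visits cost-effective, on lymphedema treatment cost alone, without the nursing cost that the analysis plan lists separately

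*Combined protocol and SAP*

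**What the plan says.** Hypothesis 6 (Hypotheses of the study) reads: "The mean cost of the intervention group at home visits, will be lower than in the control group".

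The Statistical analysis plan section describes two cost components and defines them apart from each other.

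- **Nursing programme:** "The costs of the nursing interventions included time spent by the researcher at home visits, transportation for these visits, reminders on the phone", followed by education material and tape measures.
- **Lymphedema treatment:** a projected cost, described as "Costs of treatments likely to be given for lymphedema in the intervention group and the control group due to the potential incidence of this condition". It covers hospital care of stage I/II disease in the arm, and of this figure the section says "It was based on opinions of three experts".

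The section also names a perspective ("To calculate the costs from the perspective of Social Security Institution") and a price source, and adds: "The expenses directly made by the patients were determined by the mean value of prices obtained from three national firms". It does not say how the components are combined, or how the between-group difference in cost is to be estimated.

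The closing paragraphs of the Ethical aspects section then report this result: "cost of treatment for lymphedema in the intervention group was four times as low as that in the control group, which confirmed the sixth hypothesis". From this, the next sentence concludes: "The finding indicated that follow-up of women having breast surgery through home visits is a cost-effective practice".

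**The concern.** The only evidence offered for either conclusion is the treatment-cost ratio. In the plan's own terms, that label excludes the cost of delivering the programme. A preventive programme is paid for in every woman who receives it, while the treatment saving arises only through the women in whom lymphedema is avoided. A lower treatment bill is therefore one side of the account.

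The stated inference cannot tell a reader whether home visits save money. The cost-effectiveness claim goes further still: it needs total cost set against an effect, and the text does neither. A funder or health service could act on either sentence.

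**Working it through.** **Reproducing the stated figure.** The four-fold ratio cannot be rebuilt. The documents give no unit cost, no lymphedema count by group and no nursing cost. What can be checked is what the ratio implies once the second component is added.

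**Inputs**
- Treatment cost ratio, control to intervention: 4 to 1 (Ethical aspects, closing text).
- Group sizes: 37 intervention, 35 control (Sample size calculation).
- C = control group's mean treatment cost per woman (amount not given).
- N = added nursing cost per woman in the intervention group, over any such cost in controls (amount not given).

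**Break-even if the ratio is per woman**
- Intervention total per woman = C/4 + N; control total per woman = C.
- The intervention total is lower only if N < C − C/4 = 0.75C, that is, **75.0% of C**.

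**Break-even if the ratio is of group totals**
- Control treatment total = 35C, so intervention treatment total = 35C/4.
- Per intervention woman: 35C/(4 × 37) = 0.236C.
- The intervention total is lower only if N < (1 − 35/148)C = 0.764C, that is, **76.4% of C**.

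**Total-cost ratio, intervention to control (per-woman case) = 0.25 + N/C**

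| N/C | Total-cost ratio |
|---|---|
| 0.10 | 0.35 |
| 0.50 | 0.75 |
| 0.75 | 1.00 |
| 1.00 | 1.25 |
| 1.50 | 1.75 |

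**What 75% of C means in scale (illustration only).** C is averaged over all control women, including those without lymphedema. Assume C = control incidence × cost of one treated case, T. The break-even N is then 0.75 × incidence × T. With incidences quoted in the Background:
- 5%: 0.75 × 0.05 = 3.75% of T
- 21.4%: 0.75 × 0.214 = 16.1% of T
- 42.4%: 0.75 × 0.424 = 31.8% of T

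That sum would have to cover the nursing content of three home visits averaging 45 minutes, travel, weekly reminders and materials. The Background incidences come without a follow-up period, whereas measurement here ends at six months, so they indicate scale and do not estimate this trial's incidence.

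**Reading the wording of hypothesis 6.** Its phrasing is loose. Read as mean total cost, it needs N + C/4 against C. Read as the cost of home visits only, it needs N. Treatment cost alone answers neither reading.

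**The case against.** The best defence is that the quoted sentences are discussion-style text and not the plan itself. The plan does cost the nursing programme. The sentence on treatment cost may be shorthand for a fuller result, and a figure at the end of the Statistical analysis plan section is not visible. This has force: nursing cost is missing from the stated justification, but it cannot be called missing from the plan. It does not rescue the inference, because the closing text uses the same term that the plan reserves for hospital treatment, and nothing visible says that nursing cost was included.

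Three stronger readings might be inferred, and the documents do not support them.

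- **That the programme costs more, or that hypothesis 6 is false.** Without N or C the direction is unknown. A small N would confirm the hypothesis.
- **That the treatment saving is itself within chance.** No case counts are given and the treatment cost is described as projected. An interval built on assumed counts would describe the assumption, not this trial.
- **That patient-paid expenses were wrongly included.** Two price sources for two payers is a reasonable reading. The fair remark is only that their place in the total is unstated.

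The Randomization section's 100 per group against 37 and 35 is a separate matter. Equal groups give 75.0% and the 37 and 35 split gives 76.4%, so it barely affects this point.

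**Conclusion.** The point stands as a non sequitur in the document: neither the confirmation of hypothesis 6 nor the cost-effectiveness claim follows from the reason given. The gap is potentially decisive, since an added nursing cost at or above 75% of C (76.4% on group totals with 37 and 35 women) would remove or reverse the advantage in total cost. The result assumes only that the reported ratio is exactly four and that hypothesis 6 concerns total cost; the 76.4% figure also assumes the 37 and 35 group sizes. The conclusion is unsupported as written and has not been shown to be wrong. The absence of a stated rule on patient-paid expenses, and on the programme given to controls after month six, is lesser missing detail that affects what the total contains.

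**What to change.** 1. Base the hypothesis 6 comparison on mean total cost per woman, nursing programme plus lymphedema treatment. Label this as a clarification made after results were known, since the document already reports the outcome.
2. Report nursing, treatment and total cost by group, with an interval for the between-group difference in total cost. With a single unit cost per case, that interval will reflect mainly the number of lymphedema cases, so add a sensitivity analysis that varies the expert-based treatment cost.
3. State whether patient-paid expenses, and the interventions given to controls after month six, are counted.
4. Call the programme cost-effective only if total cost is lower with no worse effect, or if cost is set against a named effect measure such as lymphedema cases avoided.
5. Until then, limit the closing text to a lower lymphedema treatment cost and delete both the confirmation of hypothesis 6 and the cost-effectiveness claim.

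The wording change costs almost nothing. Summing the components is cheap, because the plan says both were costed. The interval and the sensitivity analysis need somewhat more work, and the documents do not say whether costs were recorded for each woman. The price is a cost claim that may be less favourable or less certain.

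### Hypothesis 6 is declared confirmed, and home visits cost-effective, from a point ratio of treatment cost, with no planned comparison of cost between arms and no measure of uncertainty

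*Combined protocol and SAP*

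**What the plan says.** Hypothesis 6 (Hypotheses of the study) is directional only: "The mean cost of the intervention group at home visits, will be lower than in the control group". It names no margin, test or error rate.

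The second paragraph of the Statistical analysis plan describes how costs were built. The treatment side is "Costs of treatments likely to be given for lymphedema in the intervention group and the control group due to the potential incidence of this condition", priced for one person with stage I/II disease; of this the plan says "It was based on opinions of three experts". The nursing side is itemised: "The costs of the nursing interventions included time spent by the researcher at home visits, transportation for these visits, reminders on the phone", plus education material and a tape measure. No amounts appear for either side.

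The first paragraph of that section lists the tests. The main between-group line is "Multifactorial variance analysis of repeated measures was used to compare the groups in terms of dependent variables"; the others are pretest–posttest comparisons and corrected t-tests on mean scores. Cost is not named in any of them.

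The closing text under Ethical aspects then says that treatment cost in the intervention arm was "four times as low as that in the control group, which confirmed the sixth hypothesis", and concludes that follow-up by home visit is cost-effective. No case counts, cost totals, standard deviation, interval or p-value accompany the statement.

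**The concern.** A named study hypothesis is treated as settled because one point estimate is below another. That rule has no error control: with no effect at all, one of the two arms will almost always have the lower cost. If cost per woman follows the number of lymphedema cases, the ratio depends on counts that may be small in groups of 37 and 35, and its sampling error could be large. The reader cannot judge this, because neither the counts nor an interval is given. The conclusion also carries the document's policy message on cost-effectiveness.

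The listed tests do not readily fill the gap. They suit scale scores measured at baseline, three months and six months, whereas the cost described has no pretest and no repeated measurement.

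**Working it through.** **The plan's own figure.** The four-fold ratio cannot be reproduced, because cases per arm, unit cost and cost totals are not given. What can be checked is how informative such a ratio would be.

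**Inputs.** Group sizes are 37 and 35 (Sample size calculation). The Randomization section says 100 per group; 37 and 35 are used here because the sample-size section gives them as the groups formed. The Background gives incidences of 13.4%, 21.4% and 42.4%. Rates of 5%, 10% and 50% are added as assumptions to widen the range.

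**Model (an assumption).** Treatment cost per woman = cases × one unit cost ÷ n. Cases are independent binomials, Bin(37, p) and Bin(35, p), with the same p in both arms (no effect). Probabilities are exact sums over the joint distribution.

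**1. How often is the intervention arm's treatment cost lower by chance?** This is P(X₁/37 < X₂/35).

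| Incidence | 5% | 10% | 13.4% | 21.4% | 42.4% | 50% |
|---|---|---|---|---|---|---|
| P(lower) | 0.57 | 0.55 | 0.53 | 0.51 | 0.48 | 0.50 |

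**2. The same with nursing cost added.** Let nursing cost per woman be k times the treatment cost of one case (k is assumed; the documents give no amount). This is P(X₁/37 + k < X₂/35). At 21.4% incidence it is 0.29 for k = 0.05, 0.13 for k = 0.10 and 0.02 for k = 0.20.

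**3. How often does a finite ratio of four or more arise by chance?** This requires at least one intervention case and X₂/35 ≥ 4·X₁/37. The result is 2.8% at 5% incidence, 4.2% at 10%, 0.6% at 21.4% and about 0 at 42.4%. If trials with no intervention cases are also counted, the figure at 5% is 15.3%; the other 12.5 points are trials in which the ratio is infinite.

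**4. What interval would surround a ratio near four?** Ratio R = (b/35)/(a/37), with a intervention and b control cases. Its log has SE = √(1/a − 1/37 + 1/b − 1/35), and the 95% CI is R·exp(±1.96·SE). For a = 1, b = 4: R = 0.1143/0.0270 = 4.23 and SE = 1.093.

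| Cases (int. v control) | Ratio | 95% CI | Fisher p (two-sided) |
|---|---|---|---|
| 1 v 4 | 4.2 | 0.50–36 | 0.19 |
| 2 v 7 | 3.7 | 0.82–16.6 | 0.081 |
| 2 v 8 | 4.2 | 0.96–18.6 | 0.043 |
| 3 v 12 | 4.2 | 1.3–13.7 | 0.009 |
| 4 v 15 | 4.0 | 1.5–10.8 | 0.003 |

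At 2 v 8 the log-method interval just includes 1 while the exact test falls just below 0.05, so that row is borderline. At a control incidence of 21.4%, 0.214 × 35 ≈ 7.5 cases would be expected, which is the 2 v 7 to 2 v 8 region. At 42.4%, 0.424 × 35 ≈ 15 would be expected, which is the 4 v 15 row.

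**The case against.** The strongest reply is that a four-fold ratio is not what chance usually produces. All participants had axillary dissection and radiotherapy. The Background cites 42.4% for irradiated women after dissection and 21.4% from a meta-analysis; at those rates a four-fold ratio by chance is very rare (about 0 and 0.6%). This stands. A reader might infer from the 15% at 5% incidence that the ratio is probably noise. The documents do not support that: most of that figure comes from trials with no intervention cases, whereas the ratio reported is finite. Incidence by six months could be below the cited rates, but the documents do not say.

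Second, a reader might infer that hypothesis 6 as worded is met half the time with no effect. That holds only for treatment cost alone. The hypothesis refers to cost at home visits and the plan itemises nursing cost as well; with that added, the chance falls. Treatment cost alone is, however, the quantity the closing text uses for confirmation.

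Third, the cost may be modelled from potential incidence and expert prices rather than recorded per woman, so an analysis of per-woman data may not be possible. This is a fair limit, and the fix allows for it. If unit cost is fixed, a test of treatment cost alone also largely repeats the incidence comparison of hypothesis 5.

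Fourth, the document prints no result tables for any hypothesis, so the missing interval may reflect non-reporting, and economic results may properly be descriptive. That lowers the severity. It does not rescue the word confirmed, which is not a descriptive statement.

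**Conclusion.** The concern holds in a limited form. The plan contains no between-arm cost comparison and no measure of uncertainty, yet hypothesis 6 is declared confirmed and home visits cost-effective from a point ratio. Applied to treatment cost alone, the criterion of a lower mean would be met by chance in about 48–57% of trials, assuming 37 and 35 women, equal incidence and one unit cost per case.

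A reader might go further and conclude that the four-fold ratio is a chance result or that hypothesis 6 is false. The documents do not show this. Without case counts, the same ratio can be uninformative (1 v 4), borderline (2 v 8) or clearly different from no effect (3 v 12 and above). The claim is unsupported as written, not refuted. This should be fixed before the cost conclusion is relied on.

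**What to change.** In the Statistical analysis plan, add a cost comparison:

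- Report lymphedema cases and cost per randomised woman by arm. Cost is treatment plus nursing cost, with zero treatment cost for women without lymphedema.
- Give the difference in mean cost with a 95% bootstrap interval, resampling within each arm.
- Give a permutation p-value obtained by reshuffling arm labels across all women. Permuting within arms would leave the difference unchanged and test nothing.
- Repeat the analysis over the range of the expert-based unit cost.
- Call hypothesis 6 supported only if the interval for intervention minus control lies wholly below zero and the permutation p-value is below 0.05. Both are needed because the percentile bootstrap is optimistic with few cases: at 2 v 7 it excludes zero for treatment cost, while Fisher p is 0.081.

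Until this is done, or if per-woman costs cannot be built because the cost is purely modelled, replace the statements under Ethical aspects that the hypothesis was confirmed and that the practice is cost-effective with a statement that the cost result is descriptive.

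The cost is a short reanalysis where per-woman costs can be built, or a change of wording where they cannot. The cost claim may become weaker.
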